This study includes a two-group randomized trial. Children referred to the study (through school medical alert forms and healthcare provider referrals) will be systematically screened for asthma severity or control, and 360 eligible children will be assigned randomly to either the TEAM-UP intervention (directly observed administration of preventive asthma medications and ongoing monitoring and tailoring of the care regimen using asthma specialist-directed telemedicine visits) or the EC comparison condition (asthma screening with symptom reports and guideline-based recommendations for preventive medications, as well as systematic feedback to the PCP and caregiver to promote appropriate follow-up care). Randomization will be stratified by 1) ever seeing an asthma specialist and 2) use of a preventive asthma medication at baseline. A permuted block design will be used to assure an equal balance of children in each group over time. Following randomization, children will be followed prospectively and systematically for one year.

Subjects and Setting:

Children 4-12 years of age living in the City of Rochester and surrounding suburbs will be screened for eligibility. A total of 360 children will be recruited into the study at the beginning of each school year over 4 years. Children from approximately 50 or more schools will participate and each child will participate over 1 year.

In addition to the 360 children that will be recruited into the study, we will also include 360 primary caregivers, as well as approximately 50 school nurses, school administrators, primary care providers, and specialist providers, for a total of approximately 770 subjects. For the subset of teen children, we will also enroll 10-30 teens (12-16 years) and their caregivers. The updated total will be approximately 830 subjects.

Inclusion Criteria [1 AND 2 AND 3 AND (4 OR 5) must be met]:

1. Physician-diagnosed asthma (based on parent report with validation from the child's physician).
2. Age ≥ 4 and ≤ 12 years. (Subset of 12-16 year olds)
3. Residence in the City of Rochester and surrounding suburbs, with a primary residence within the following zip codes: 14445, 14604, 14605, 14606, 14607, 14608, 14609, 14610, 14611, 14612, 14613, 14614, 14615, 14616, 14617, 14618, 14619, 14620, 14621, 14622, 14623, 14624, 14625, 14626.

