4. For referrals from medical practices, if any of the 3 criteria below are met based on data obtained from a referral, then the child will be considered eligible due to their history of significant asthma and risk for future acuity, regardless of whether the caregiver-reported NHLBI symptom criteria (listed in #5 below) are met.
 - i. ≥ 2 asthma exacerbations (resulting in ED, urgent Care, or acute clinic visits) in the prior year
 - ii. ≥ 2 oral prednisone (systemic steroid) episodes in the prior year
 - iii. ≥ 1 hospitalizations for asthma in the prior year
5. Moderate-severe persistent severity (requiring Step 3 or higher care) or difficult to control asthma despite therapy (based on age-specific NHLBI guidelines¹⁰).

Moderate-Severe Persistent Severity (for children not taking a preventive medication)

- a. Age 4: Any 1 of the following:
 - i. Daily asthma symptoms (in prior 4 weeks)
 - ii. >2 days per month with nighttime awakenings
 - iii. Daily use of rescue medications for symptom control (in prior 4 weeks)
 - iv. >2 asthma episodes during the past 6 months that required systemic corticosteroids*
- b. Age 5-11: Any 1 of the following:
 - i. Daily asthma symptoms (in prior 4 weeks)
 - ii. >1 day per week with nighttime awakenings
 - iii. Daily use of rescue medications for symptom control (in prior 4 weeks)
 - iv. >2 asthma episodes during the past 6 months that required systemic corticosteroids*
- c. Age 12: Any 1 of the following:
 - i. Daily asthma symptoms (in prior 4 weeks)

- ii. >1 day per week with nighttime awakenings
- iii. Daily use of rescue medications for symptom control (in prior 4 weeks)
- iv. >2 asthma episodes during the past 6 months that required systemic corticosteroids*

*adapted from NHLBI guidelines and based on specialist recommendations

Not Well Controlled (for children taking a preventive medication)

- a. Age 4: Any 1 of the following:
 - i. >2 Days/week with asthma symptoms (in prior 4 weeks)
 - ii. >1 day per month with nighttime awakenings
 - iii. >2 Days/week use of rescue medications for symptom control (in prior 4 weeks)
 - iv. ≥2 asthma episodes during the past year that required systemic corticosteroids
- b. Age 5-11: Any 1 of the following:
 - i. >2 Days/week with asthma symptoms or multiple times a day on ≤2 days/week (in prior 4 weeks)
 - ii. ≥2 days per month with nighttime awakenings
 - iii. >2 Days/week use of rescue medications for symptom control (in prior 4 weeks)

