Participants will be given the option to allow future contact for other research studies at the time of consent. All participants who provided permission will be added to a future contact database dedicated to childhood asthma research (RSRB #31010).

For the teen subgroup, we have requested a waiver of documented consent, as the data collection will be minimal, the intervention is to implement guideline-based care with specialists via telemedicine, and we will not be implementing directly observed therapy (DOT) in school, as we do for the younger children. We will obtain verbal approval from both the caregiver (screening script) and teen (assent script) for this subgroup.

Randomization:

After the baseline assessment, each child will be randomly assigned to either the TEAM-UP or EC group. Randomization will be stratified by 1) ever seeing an asthma specialist and 2) use of a preventive asthma medication at baseline. Due to the seasonality of asthma, we will use a permuted block design to assure an equal balance of children in each group over time. The randomization scheme will be independently developed by the Biostatistics Center, and will be implemented via REDCap™. All families will receive an educational packet including asthma information, smoking cessation resources, and information about local asthma and community resources. Once randomized, the research team will send a symptom report and notification of enrollment to each child's PCP (see below)

All Study Children:

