SFD to be 3.6 and within-subject correlation (ICC) of 0.3. We calculated power for the intervention effect on SFD while justifying repeated assessments for outcomes.^{64,65} A sample size of 150 subjects per group will obtain 90% power to detect a difference of 0.8 SFD, and 80% power to detect a difference of 0.7 SFD at a two-sided 5% significance level. This difference would be clinically meaningful and consistent with prior successful interventions.^{7,66-68} We found that 194 of the children from our prior SB-TEAM study had moderate-severe persistent or difficult to control asthma at baseline, and would be eligible for TEAM-UP. In addition, in our prior office-based study we enrolled >400 children with moderate-severe asthma from the main primary care practices in urban Rochester over 4 years. Our prior studies enrolled >70% of eligible subjects. Thus, we can conservatively enroll 90 subjects/year, which is more than adequate for sample size requirements. We anticipate <15% attrition (attrition <5% in prior studies). We therefore expect complete data on at least 150 children per group.

Primary Analysis:

The primary analysis of this study aims to assess the effectiveness of the TEAM-UP intervention in reducing asthma morbidity (including symptom-free days post-intervention (follow-ups at 3 mo, 5 mo, 7 mo and 12 mo as the primary outcome) compared to an enhanced care comparison group in school age children with moderate-severe persistent asthma or uncontrolled asthma. We will use graphs and descriptive statistics to summarize the primary and secondary outcomes by intervention group at each assessment point (baseline, 3, 5, 7 and 12 mos). We will assess for differences between groups at baseline despite randomization in key characteristics (i.e.; age, race, ethnicity, insurance, caregiver education, smoke exposure.) These comparisons will enable the identification of covariates to be controlled when evaluating the treatment effect. If distributional assumptions associated with a particular statistical procedure are violated, appropriate transformations will be made or non-parametric alternatives used. In accordance with the intention-to-treat principle,⁶⁹ all randomized subjects will be analyzed within the group to which they were assigned. Minimal crossover is expected. Hypothesis-driven comparisons will be made to control the family-wise type I error rate at 0.05 (two-sided) for the primary hypothesis.

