For the primary outcome analysis, the time-course of treatment effect on SFD during the follow-up period will be evaluated using a linear mixed model (LMM) accounting for repeated measures within each subject to test the intervention effect of TEAM-UP over time, with SFD as the dependent variable, and intervention group and group by time interaction as independent variables.⁷⁰ The treatment effect will be regarded as fixed and the subjects as the random effect, with appropriate variance covariance structure specified. Interaction effects between intervention and follow-up periods are included to catch possible differences in how SFD changes over time between intervention groups. Post treatment effects and maintenance gain from short to long term will be assessed by specifying appropriate linear contrasts. Baseline SFD and factors that differentiate between groups will be included as covariates. Model fitting statistics such as Information Criteria and difference in log likelihood will be used for model selection. Standard measures such as residual plots will check goodness-of-fit of the regression model assumptions and identify outliers. We will calculate intraclass coefficient (ICC) within providers (specialist and PCP); if autocorrelation is significant, provider will be included as another level of random effect in the mixed model to account for the nested data structure. If the outcome measure violates the normal assumption required by LMM, we will evaluate the intervention effect using Generalized Estimating Equations (GEE).⁷¹ By specifying marginal mean effects of independent variables on the outcome variable, GEE offers consistent and robust estimates but does not require specification of a fully parametric distribution. Other continuous outcomes (days/nights with symptoms, quality of life, etc.) will be analyzed similarly. Discrete outcomes will be analyzed by fitting Generalized Estimating Equation model. Appropriate link functions and response probability distributions will be specified.

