specialists, and school members to evaluate *Adoption*. We will conduct a survey of providers and school staff following the intervention to gauge their reaction to the intervention components and their willingness to support them in the future. To assess *Implementation* we will use check-lists, tracking logs, surveys and chart reviews to measure the extent to which participants partook in each program component (telemedicine visits, guideline-based adjustments, % medication doses delivered at school, and/or through video supported DOT). To assess *Maintenance* we will use surveys and open-ended questions to evaluate plans for continuation (or modification) of each intervention component post-study, and we will use 12-month follow-up data to analyze long-term effects on primary outcomes and QOL.

COVID-19

In response to the COVID-19 pandemic, we will follow the Human Subjects Research guidelines outlined by the University of Rochester to continue enrollment for this study. Please find the following link for these guidelines: <https://www.urmc.rochester.edu/coronavirus/coronavirus-research/guidance-for-researchers/human-subjects-research.aspx>. We will minimize in-person contacts to only those tasks necessary to conduct the research (e.g., obtaining consent, review medications and forms). We will ensure that team members are appropriately trained in safety measures, maintain social distancing when possible, use personal protective equipment for themselves and research subjects (and family members), and will ensure proper cleaning/sanitizing of hands, equipment and workstations. We will continue to monitor and follow the updated guidelines put forth by the UofR in the link above.

The intervention may look different during the COVID-19 pandemic. If schools are open, participants in the Intervention group may receive directly observed therapy (DOT) of their preventive asthma medication supervised by the school nurse or health aide. Additionally, they may receive telemedicine visits at school. However, if schools are not fully open or by family preference, we will support families with ongoing medication adherence, which will include school-based and/or video supported DOT. Additionally, providers may conduct telemedicine visits without the data obtained by clinical telehealth assistants onsite using Zoom or another HIPAA compliant method to remotely connect with families.

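### Beyond baseline SFD, the primary model takes its covariates from chance baseline imbalance and does not name the two randomisation strata; the loss is small and nearly free to avoid

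*Combined protocol and SAP*

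**What the plan says.** The Study Design and Randomization sections set out the allocation: "Randomization will be stratified by 1) ever seeing an asthma specialist and 2) use of a preventive asthma medication at baseline". Study Design adds: "A permuted block design will be used to assure an equal balance of children in each group over time". Block size is not given.

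Under Primary Analysis, the arms are compared at baseline on six listed characteristics: age, race, ethnicity, insurance, caregiver education and smoke exposure. Neither stratification factor is on that list. The stated purpose is: "These comparisons will enable the identification of covariates to be controlled when evaluating the treatment effect". No test or threshold defines a difference.

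The model itself is a linear mixed model with group, group by time and a random subject effect. On covariates it says "Baseline SFD and factors that differentiate between groups will be included as covariates". The next sentence adds "Model fitting statistics such as Information Criteria and difference in log likelihood will be used for model selection", without saying whether this covers covariates, the covariance structure or both.

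**The concern.** Under randomisation, an observed baseline difference between arms is chance. Its size says nothing about how well the characteristic predicts the outcome, and precision comes from adjusting for variables that do predict it. A rule that selects on imbalance therefore selects on the wrong property. It works particularly badly for the stratification factors, because blocking within strata removes the imbalance that the rule looks for.

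Two things follow:

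- **Precision.** Stratifying removes between-stratum variation from the true sampling variance of the treatment effect. A model without the strata leaves that variation in the residual. If the strata are prognostic, the reported standard error exceeds the true one, the confidence interval is wider than the design supports, and the test runs below its nominal level.
- **Prespecification.** The rest of the covariate list is not settled until baseline differences have been inspected, and the cut-off is left open. If model selection by fit statistics also covers covariates, the list is settled only after outcomes have been fitted.

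**Working it through.** **Inputs from the documents** (Sample Size and Power Justification): SD 3.6, within-subject correlation 0.3, four follow-ups (3, 5, 7 and 12 months), 150 children per group with complete data, two-sided 5%.

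**Assumptions, because the documents give no value:** R², the share of the variance of a child's mean SFD left after baseline SFD that the two strata explain; and r, the correlation of baseline with each follow-up. The main case is r = 0.3, which applies the plan's within-subject correlation to baseline as well.

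**The plan's own power.** The plan states 90% for 0.8 SFD and "80% power to detect a difference of 0.7 SFD at a two-sided 5% significance level".

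- Variance of the mean of four follow-ups: 12.96 × (1 + 3 × 0.3)/4 = 12.96 × 0.475 = 6.16.
- Adjusted for baseline at r = 0.3: 12.96 × (0.475 − 0.09) = 4.99.
- Standard error: s = √(2 × 4.99/150) = 0.258.
- Power: Φ(0.8/0.258 − 1.96) = 87.3%, and 77.5% at 0.7 SFD.

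This is 2.7 and 2.5 points below the stated 90% and 80%. The detectable differences at those powers are 0.836 and 0.723, which round to the stated 0.8 and 0.7. The gap is a separate matter, and the baseline-adjusted variance serves as the starting point here.

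**Would the rule select the strata?** In simulated stratified block allocation (blocks of 4, 6 and 8), with a difference taken as p<0.05 (an assumed cut-off), neither factor was selected in any of 264,000 trials. By contrast, six independent unstratified characteristics give a chance of at least one selection of 1 − 0.95⁶ = 26% at p<0.05, or 1 − 0.90⁶ = 47% at p<0.10.

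**Cost of leaving out balanced strata.** The reported standard error is s and the true one is s√(1 − R²). So:

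- Type I error = 2Φ(−1.96/√(1 − R²))
- Power, strata omitted = Φ((d − 1.96s)/(s√(1 − R²)))
- Power, strata included = Φ(d/(s√(1 − R²)) − 1.96)
- 95% CI half-width = 1.96s omitted, and 1.96s√(1 − R²) included

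Results at r = 0.3:

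| R² | Reported SE too large by | Type I error, omitted | CI half-width, omitted v included | Power at 0.8, omitted v included | Power at 0.7, omitted v included |
|---|---|---|---|---|---|
| 0 | 0% | 5.0% | 0.506 v 0.506 | 87.3% v 87.3% | 77.5% v 77.5% |
| 0.02 | 1.0% | 4.8% | 0.506 v 0.500 | 87.6% v 88.0% | 77.7% v 78.3% |
| 0.05 | 2.6% | 4.4% | 0.506 v 0.493 | 87.9% v 88.9% | 78.0% v 79.5% |
| 0.10 | 5.4% | 3.9% | 0.506 v 0.480 | 88.6% v 90.5% | 78.7% v 81.6% |

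At R² of 0.02, 0.05 and 0.10, the loss at 0.8 SFD is 0.5, 1.4 and 2.7 points if r = 0 (s = 0.287), and 0.1, 0.2 and 0.3 points if r = 0.5 (s = 0.197).

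**Check by simulation** (300 children, blocks of 4, factor prevalences 40% and 60%, 6,000 trials per case, Monte Carlo error 0.3 points on type I error). At R² of 0, 0.02, 0.05 and 0.10, type I error was 4.5, 4.8, 4.4 and 3.8% with strata omitted, and 4.4, 5.0, 4.9 and 5.0% with them included. Power loss at 0.8 SFD was 0.0, 0.3, 1.0 and 2.0 points, in line with the formulas.

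**What each R² requires.** Assume the two factors are independent, have equal effects, and have prevalences of 40% and 60% (variance 0.24 each). Each must then shift mean follow-up SFD, beyond baseline SFD, by √(R² × 4.99/0.48) = 0.46, 0.72 or 1.02 days for R² of 0.02, 0.05 or 0.10. The last exceeds the 0.8 SFD target effect.

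**If fit statistics chose the covariates.** With noncentrality 300 × (R²/2)/(1 − R²), a given factor would be kept by AIC in 63% of trials and by BIC in 26% at R² 0.02, and in 92% and 66% at R² 0.05. That route would not fix the model in advance either.

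**The case against.** The strongest reply is that nothing here is invalid and the loss is slight. The test is conservative, and at R² of 0.02 to 0.05 the half-width improves by only 0.006 to 0.013 SFD. Every non-zero loss rests on an R² that the documents do not supply. A fixed stratum can explain only between-child variance, which at r = 0.3 is 12.96 × (0.3 − 0.09) = 2.72 of the 4.99. R² of 0.10 would thus be 18% of everything that could be explained. Part of any medication effect may also already run through baseline SFD, since the Inclusion Criteria set different symptom thresholds for treated and untreated children. All of this stands. It is why 0.10 is an upper end and why the point concerns efficiency and prespecification. The extreme values of r (0 and 0.5) also fit poorly with an exchangeable correlation of 0.3, and only bound the result.

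A second reply is that the candidate list is largely named in advance, that selection uses baseline data only, and that adjusting for a chance imbalance in a prognostic variable can be sensible. This stands in part. The six characteristics are named, but the cut-off is not, imbalance remains a poor guide to prognosis, and the strata are not on the list.

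A third reply is that the model-selection sentence may refer only to the covariance structure. That is possible. In that case the stated rule has no route by which the strata would normally enter.

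**Conclusion.** The concern holds. The trial randomises within two factors that its stated primary model does not name, and the rule for adding covariates would almost never add them. If the factors are not prognostic beyond baseline SFD, essentially nothing is lost. If they are, then at r = 0.3 and R² from 0.02 to 0.10 the reported standard error is 1.0% to 5.4% too large, the true type I error is 4.8% to 3.9%, and power falls by 0.4 to 1.9 points at 0.8 SFD. These sizes depend on assumed values of R² and r. The direction does not: the error is conservative, with no bias and no excess of false positives. The change is worth making because it can gain a little and costs almost nothing. It also settles the covariate list in advance in a trial where participants know their allocation.

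**What to change.** In Primary Analysis, replace the covariate sentence with wording such as:

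> The primary model (LMM, or GEE/WGEE if used) will adjust for baseline SFD and for both randomisation factors: prior asthma-specialist care (ever or never) and preventive-medication use at baseline (yes or no). Any further covariate will be named for its expected prognostic value before outcome data are seen by arm.

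Delete the sentence that uses the baseline comparisons to identify covariates, and keep those comparisons descriptive. If the sponsor wants any of the six listed characteristics in the model, they should be named now on prognostic grounds. Adjustment for observed imbalance can remain as a sensitivity analysis.

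The cost is a short protocol/SAP amendment and two degrees of freedom (three if the strata enter as four cells) out of about 300 children. Both factors must already be recorded in order to randomise, so no new data are needed. The COVID-19 section describes arrangements "to continue enrollment for this study", which indicates that recruitment had begun, so the amendment should be made before outcome data are seen by arm.

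### The deciding test for symptom-free days is left to fit statistics and unreconciled distributional fallbacks, so neither the 5% error claim nor the day scale is assured

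*Combined protocol and SAP*

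**What the plan says.** All of this stands in the combined protocol and SAP, under Analysis, Primary Analysis.

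- **Error control.** The opening paragraph says: "Hypothesis-driven comparisons will be made to control the family-wise type I error rate at 0.05 (two-sided) for the primary hypothesis".
- **Default model.** The next paragraph names a linear mixed model (LMM) "with SFD as the dependent variable, and intervention group and group by time interaction as independent variables". Baseline symptom-free days (SFD) is a covariate, together with whatever factors are found to differ between the groups. The text describes the group-by-time terms as part of the model.
- **Selection.** "Model fitting statistics such as Information Criteria and difference in log likelihood will be used for model selection". Neither the candidate models nor a decision rule is given. The LMM comes "with appropriate variance covariance structure specified", but the structure is not named. Linear contrasts are promised but not defined. A provider random effect enters only if provider clustering proves significant.
- **Fallback for the primary outcome.** "If the outcome measure violates the normal assumption required by LMM, we will evaluate the intervention effect using Generalized Estimating Equations (GEE". No test, threshold or link function for SFD is given.
- **General fallback, in the opening paragraph.** "If distributional assumptions associated with a particular statistical procedure are violated, appropriate transformations will be made or non-parametric alternatives used".

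The section describes no blinded model-building step and no model lock. It does not require the primary result to be reported on untransformed SFD.

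**The concern.** An error rate belongs to a complete procedure: which model, which hypothesis, which statistic. Here the outcome data may shape the model, and the text does not say which test then decides the trial. That could be an average group difference over the four visits, a joint test of group and group-by-time, or a contrast at a particular visit. If the data also choose among these, the 5% claim fails.

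The second problem is the scale. A violated distributional assumption has two different remedies in the same section. One, GEE, can still give a mean difference in days. The other, a transformation or a non-parametric method, generally cannot. The sample size is built on a difference of 0.8 SFD, so a primary result on a log or rank scale would not estimate the quantity for which the trial was powered.

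**Working it through.** **Inputs from the documents.** Two-sided 5% (Primary Analysis). Four follow-ups at 3, 5, 7 and 12 months, 150 children per group, SD 3.6 and within-subject correlation 0.3 (Sample Size and Power Justification). With four visits the group-by-time interaction has 4 − 1 = 3 df, and the joint test of group plus interaction has 1 + 3 = 4 df.

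**Assumptions.** The documents do not give the SFD recall window. The simulations used a 0–14 scale with underlying mean 7 or 10, and an unbounded normal outcome for comparison. Data were complete and the analysis was baseline-adjusted. There were 4,000 null trials per scenario, so the Monte Carlo standard error at 5% is √(0.05 × 0.95/4000) = 0.0034, about 0.35 points.

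**1. The plan's own 5%, with one fixed analysis.** Testing the average group effect on untransformed SFD gave 4.5–4.8% type I error, or 4.7–5.1% with robust standard errors. The 5% claim is therefore attainable, including on a bounded scale.

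**2. Data-driven rules that leave the tested effect alone.**

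| Rule | Simulated type I error |
|---|---|
| AIC chooses the covariates | 4.7–5.1% |
| Covariates picked by baseline imbalance | 4.6–4.9% |
| Shapiro–Wilk gate to a rank test | 4.3–5.0% |
| Shapiro–Wilk gate to a log transform | 4.6–4.9% |

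None of these inflates. Covariance selection was not simulated. It leaves the tested contrast unchanged, so it creates no extra route to a positive result.

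**3. Rules that change the tested effect.** Under the null with balanced data, let A be the average-effect statistic, chi-square with 1 df, and B the interaction statistic, chi-square with 3 df, independent of A. Suppose A is tested against 3.84 when the interaction is dropped, and A + B against 9.49 (4 df) when it is kept.

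- *AIC* keeps three extra parameters if B > 2 × 3 = 6, which has probability 0.1116. Error = 0.05 × 0.8884 + P(B > 6 and A + B > 9.49) = 0.0444 + 0.0400 = **0.0844**. Simulated trials gave 8.2%.
- *A 5% likelihood-ratio rule* keeps the interaction if B > 7.81, which has probability 0.05. Error = 0.05 × 0.95 + 0.0334 = **0.0809**.
- *Success on either the main effect or the interaction*: 1 − 0.95² = **0.0975**. Simulated trials gave 9.1–9.9%.
- *Average effect tested whichever model is kept*: 0.05 × 0.8884 + 0.05 × 0.1116 = **0.05**.

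The excess comes entirely from switching or adding tests, not from model selection as such.

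**4. Whether the normality trigger fires.** A bounded day count cannot be exactly normal, but the plan names no test. With Shapiro–Wilk at 5% on the residuals of the four-visit mean, the trigger fired in 6.5% of trials at mean 7, 69.8% at mean 10 and 5.2% for the normal outcome. It depends on a distribution that the documents do not describe.

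**5. Scale after the trigger.** GEE with an identity link estimates a mean difference in SFD. A rank test or a log-scale model does not. Any scale problem therefore comes from the general transformation/non-parametric sentence, not from the GEE fallback.

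**The case against.** The strongest reply is that the primary model is largely named: an LMM with SFD as outcome, group, group-by-time and baseline SFD. The text presents the interaction as part of the model, so fit statistics may be meant only for the covariance structure, the covariates or the provider level. No 4-df joint test appears anywhere, and one of the sample-size references concerns a time-averaged difference. On that reading the error rate stays at about 5%. This stands, and it is why 8% and 10% cannot be presented as the plan's error rate. It does not settle the matter, because the plan neither limits what is selected nor says that the time-averaged contrast decides.

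It can also be said that the transformation sentence is general and that GEE is the specific rule for SFD. That is a reasonable reading, but the sentence stands under Primary Analysis without an exception for the primary outcome.

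Two stronger readings are tempting and not supported:

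- *That a normality failure leads to unweighted GEE with a stricter missing-data assumption.* The section's closing paragraph on missing data provides weighted GEE when missingness depends on observed responses.
- *That a transformed primary analysis would invalidate the cost-effectiveness ratio.* Cost Effectiveness Analysis defines the ratio from the difference in SFDs gained and bootstraps it. Nothing there takes that difference from the primary model.

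**Conclusion.** The concern holds as a lack of assurance, not as demonstrated inflation. If one average-effect contrast is always tested, the error rate is 5%. It would be about 8% (8.4% under AIC, 8.1% under a likelihood-ratio rule) if fit statistics also chose between a single-effect and a joint 4-df test, and about 10% if either the main effect or the interaction counted. The text does not say which applies. The chi-square figures assume balanced data and independent components. The simulations also rest on an assumed 0–14 window and complete data.

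A reader might infer that every data-driven step in the section inflates error. The checks do not show that: the covariate and normality rules stayed near 5%. The scale problem is narrower but concrete. Two unreconciled remedies cover the same violation, and one of them would leave the trial without an estimate of the 0.8-day difference used for power.

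**What to change.** State one primary analysis in the SAP:

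- An LMM on untransformed SFD, with visit as a factor and with group and group-by-visit kept regardless of fit.
- Fixed covariates: baseline SFD and the two stratification factors (past specialist care and baseline preventive medication use). Adjustment for factors found imbalanced becomes a sensitivity analysis.
- A named covariance structure, for example unstructured, with an ordered fallback for non-convergence only, and robust standard errors. Decide in advance whether a provider level belongs in the model.
- One deciding test: the average group difference over 3, 5, 7 and 12 months, two-sided 5%. Visit-specific and maintenance contrasts are secondary.

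Say explicitly that neither the transformation/non-parametric sentence nor the normality switch applies to the primary outcome. Report GEE or weighted GEE, transformed, rank and bounded-count models as labelled sensitivity analyses, with the link stated.

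The cost is wording, ideally settled before outcome data are seen by group. The team gives up later modelling freedom, and an unstructured covariance for four visits needs 4 × 5/2 = 10 parameters, which is modest for about 300 children. Unstructured is one acceptable choice among several; what matters is that it is fixed.
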